4.1 General Principles

For continuous variables, descriptive summary statistics including number of patients, mean, standard deviation, median, upper and lower quartiles (25th percentile, 75th percentile), and minimum and maximum values will be presented. For categorical variables, counts and percentages will be presented in frequency tables. For continuous variables collected at multiple time points, the descriptive statistics will be provided at each time point. All statistical tests will be conducted using 2-sided tests with 10% Type I error rate unless otherwise stated.

Placebo-treated patients will be pooled and analyzed as a single placebo group. Therefore, four treatment groups will be included and presented in the analysis as 40 mg, 80 mg, 120 mg, and placebo. Patients who are Fesomersen-treated may be pooled and summarized as the pooled treatment group.

The statistical evaluation will be performed by using the software package SAS release 9.2 or higher (SAS Institute Inc., Cary, NC, USA) or if applicable, other software.

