4.7 Sample Size Determination

No formal statistical sample size estimates were performed.

The sample size was selected based on prior experience in ESRD with the unconjugated ASO. This study is planned to ensure the safety, tolerability, and PK/PD relationships are assessed adequately while minimizing unnecessary participant exposure. There is no plan for statistical hypothesis testing for this study. In this study, the number of subjects is considered based on the ISIS 416858-CS5 study design.

Approximately 288 participants (96 [72 active+24 placebo] per cohort) will be randomly assigned to study intervention so that an estimated 240 participants will complete the main treatment period. All participants will be randomized to 1 of 3 dose cohorts in a 1:1:1 ratio (Cohort A, Cohort B, and Cohort C). Within each dose cohort, subjects will be randomized in a 3:1 ratio to receive treatment with either Fesomersen or placebo. Considering an approximately 15% dropout rate, an estimated total of 60 participants per intervention group and the placebo group will complete the main treatment period. A participant will be evaluated once he/she was randomized and received at least one dose of study intervention. The number of evaluable and randomized participants is assumed to be similar.

Table 4-1 summarizes 95% expected range for the true population proportion of participants with a composite of MB and CRNMB bleeding. For example, with 60 participants, if 5% of them had a composite of MB and CRNMB bleeding during the main treatment period and the desired confidence level is 95%, the corresponding confidence interval would be \pm 5.51, i.e. the range of 0.0 % to 10.51%. If multiple samples were drawn from the same population and a 95% CI calculated for each sample, we would expect the true population proportion to be found within 95% of these CIs.

Sample Size	Observed Proportion *	Desired Confidence level	Corresponding two-sided confidence interval	Range for the true population proportion
60	2%	95%	±3.54	0.0% to 5.54%
	3%	95%	±4.32	0.0% to 7.32%
	4%	95%	±4.96	0.0% to 8.96%
	5%	95%	±5.51	0.0 % to 10.51%
	6%	95%	± 6.01	0.0% to 12.01%
	7%	95%	± 6.46	0.54% to 13.46%
	8%	95%	± 6.86	1.14% to 14.86%

Table 4-1: Confidence Interval for proportion of participants with a composite of MB and CRNMB Bleeding

CRNMB = clinically relevant non-major bleeding, MB = major bleeding

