Maximum change in FXI activity	Main	PD	OA
levels			

Table 5-2: Sketch of the planned analyses on the endpoints

PA: Data scope according to primary analysis principle, TA: Data scope according to total treatment analysis principle, OA: Data scope according to overall analysis principle.

a) on-treatment estimand

b) treatment policy estimand

6. Statistical Methodology

The primary safety and efficacy variables will be analyzed descriptively for the following groups:

- Pooled Placebo Group (from Cohorts A, B and C),
- 40 mg Dose Group (Fesomersen from Cohort A),
- 80 mg Dose Group (Fesomersen from Cohort B), and
- 120 mg Dose Group (Fesomersen from Cohort C).

For selected analyses the pooled Fesomersen treatment arms will be presented in addition.

Incidence rates and cumulative incidences will be calculated only for endpoints with at least 1 event in a treatment arm. Hazard ratios (cause specific and sub distribution), log-rank test and Gray's test will only be calculated if there is at least 1 event in each of the compared treatment arms.

6.1 **Population Characteristics**

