$$\left[\frac{IR_{adj} * \chi^2(0.05; 2e)}{2e}; \frac{IR_{adj} * \chi^2(0.95; 2e)}{2e}\right],$$

with $\chi^2(q; 2e)$ the q quantile of a chi square distribution with 2e degrees of freedoms and e the number of participants with an event. (Nelson 1982)

Hazard ratios

With respect to the cause-specific hazards for the respective safety variable, each of the Fesomersen groups will be compared to the placebo group using two-sided log-rank tests. Due to the explorative nature of these analyses, no multiplicity adjustment will be done.

The cause-specific hazard function $h_k(t)$ is the chance that an individual experiences an event of the primary safety outcome in the next instant in time, given that the individual has not had such an event or a competing event up to time t. Cause-specific hazard ratios, cause-specific relative hazard reduction (csRHR; csRHR = $100 \times [1 - \text{cause-specific hazard ratio}]\%$), and corresponding 2-sided 90% and 95% confidence intervals, comparing the hazards for the event-of-interest in each of the Fesomersen groups with the placebo group will be estimated based on three separate cause-specific Cox proportional hazards models as exploratory amalysis. Censoring will be assumed to be independent form the study intervention. For example, for the comparison of the 120 mg Fesomersen group with the placebo group, the corresponding cause-specific Cox proportional hazards model can be described by the following equation:

$$H_k(t,x_i) = h_{0,k}(t) \exp(\beta_k x_i),$$

where

- $h_k(.)$ cause-specific hazard function for primary safety outcome, as a function of time and subject's covariates
- $h_{0,k}(.) \quad \text{unspecified underlying baseline hazard function for primary safety outcome; hazard of an individual with $x_i = 0$ }$
- t time (in days) relative to the date of first administration
- xi treatment group of subject i
 (0 corresponds to "placebo group" and
 1 corresponds to "120mg Fesomersen group")
- β_k unknown parameter (to be estimated); cause-specific hazard ratio = exp(β_k)

k type of event

Probability

As a supportive analysis, the cumulative incidence functions for the respective event-ofinterest will be compared using the Fine and Grays subdistribution hazards model as well as using the Gray's test.

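### Log-rank and Gray's tests are withheld, along with hazard ratios, whenever one compared arm has no event, although only the hazard ratio is undefined there

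*SAP*

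**What the plan says.** The introductory text of SAP section 6 sets two event-count conditions.

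- Cause-specific and subdistribution hazard ratios, the log-rank test and Gray's test "will only be calculated if there is at least 1 event in each of the compared treatment arms". No substitute is named for when the condition fails.
- A looser condition covers arm-level quantities: "Incidence rates and cumulative incidences will be calculated only for endpoints with at least 1 event in a treatment arm".

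The stricter condition governs these parts of SAP 6.4.1.1:

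- the cause-specific comparison, in which "each of the Fesomersen groups will be compared to the placebo group using two-sided log-rank tests";
- the hazard ratios, which "will be estimated based on three separate cause-specific Cox proportional hazards models";
- the supportive comparison of cumulative incidence functions, which "will be compared using the Fine and Grays subdistribution hazards model as well as using the Gray's test".

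The SAP gives these a modest status: "Due to the explorative nature of these analyses, no multiplicity adjustment will be done". SAP 4.1 nevertheless sets a level for them: "All statistical tests will be conducted using 2-sided tests with 10% Type I error rate unless otherwise stated".

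The primary analysis in SAP 6.4.1 is separate. It gives each arm's proportion with a Blaker 95% interval and each dose's difference from placebo with an exact 95% interval (Agresti and Min). Neither carries an event-count condition.

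**The concern.** A log-rank or Gray's statistic compares observed with expected events. An arm with no events still contributes an expected count and a variance, so the statistic exists as long as the pair has at least one event. What fails is the Cox or Fine-Gray estimate, whose maximum runs off to zero or infinity. The SAP treats tests and estimates alike.

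The result is outcome-dependent reporting. The comparison disappears when the hazard ratio is most extreme, in either direction: no bleeds on placebo against several on a dose, or none on a dose against several on placebo. Protocol 4.1 says the primary analysis serves Phase 3 dose selection, so both patterns would interest the reader.

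The loss matters most where nothing exact remains. SAP 6.4.3 sends the total-treatment (TA) and overall (OA) bleeding analyses to the methods of 6.4.1.1, which contain no exact difference. SAP 6.2.1 and 6.2.1.1 give the efficacy endpoints and their components per-arm Blaker intervals, rates and time-to-event methods, but no exact difference either.

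**Working it through.** **Inputs.** SAP 4.7 gives 72 active and 24 placebo participants per cohort, so 72 per dose group and 3 × 24 = 72 pooled placebo. The footnote to SAP Table 4-1 gives composite bleeding of 5.7% on placebo and 3.8%, 5.6% and 4.0% at the three doses of the unconjugated compound. The level is 10% two-sided. Rates of 3%, 2% and 1% for rarer outcomes, such as major bleeding alone or single efficacy components, are assumptions; the documents give none.

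**The plan's own figure.** Table 4-1 reproduces as 1.96 × √(p(1−p)/60). At p = 5% this is ±5.51 points, and all seven rows agree. No stated figure is in dispute.

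**1. The tests exist; the estimate does not.** Log-rank with 72 versus 72, distinct event times and no censoring, beside Fisher's exact test:

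| Events | Log-rank p (asymptotic) | Fisher p | Under the rule |
|---|---|---|---|
| 0 vs 1 | 0.317 | 1.00 | withheld |
| 0 vs 3 | 0.081 | 0.245 | withheld |
| 0 vs 4 | 0.043 | 0.120 | withheld |
| 0 vs 5 | 0.023 | 0.058 | withheld |
| 0 vs 6 | 0.013 | 0.028 | withheld |
| 1 vs 5 | 0.09 to 0.10, by position of the single event | 0.209 | reported |
| 1 vs 12 | about 0.001 | – | reported |

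For 0 vs 4 the Cox partial log-likelihood only rises: −19.84 at β = 0, −17.05 at β = 5, −17.02 at β = 20. It has no finite maximum. A one-sided bound does exist. For 0 vs 5 with equal time at risk, θ = 0.05^(1/5) = 0.549, so the lower limit of a 90% interval is 0.549/0.451 = 1.22.

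**2. How often the rule fires for the composite.** P(no event) = (1−p)^72:

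- placebo: 1.5%;
- doses: 6.1%, 1.6% and 5.3%.

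A pair is withheld with probability 1 − (1−P₀)(1−P₁), which gives 7.5%, 3.0% and 6.7%. The chance that at least one of the three pairs is withheld is 13.8%.

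**3. Rarer outcomes (assumed rates, equal in both arms).** Only pairs with exactly one empty arm matter, because 0 vs 0 has nothing to test. The probability is 2q(1−q), with q = (1−p)^72:

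| Rate | q | Exactly one arm empty | 0 vs 5 or more |
|---|---|---|---|
| 3% | 0.112 | 20% | 1.5% |
| 2% | 0.233 | 36% | 0.7% |
| 1% | 0.485 | 50% | 0.08% |

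The last column matters because, by Fisher's test, 0 vs 5 is the first pattern below 10%. At the planning rates for the composite, 0 vs 5 or more has probability 1.2% to 2.6% per pair.

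**4. The time-based contrast that may survive.** SAP 6.4.1.1 also plans the Aalen-Johansen difference with a 90% normal interval whose variance is the sum of the two arms' variances. An empty arm contributes zero. For 0 vs 3 without censoring, using the binomial variance:

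- difference 3/72 = 4.17 points;
- standard error √(0.0417 × 0.9583/72) = 2.35 points;
- interval 4.17 ± 1.645 × 2.35 = 0.3 to 8.0 points.

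This excludes zero, while Fisher's p is 0.245.

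**5. Rates.** The 90% interval for the exposure-adjusted rate in SAP 6.4.1.1 divides by 2e, where e is the number of participants with an event. It is undefined at e = 0.

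**The case against.** The strongest reply is that nothing confirmatory is lost. SAP 4.7 says "There is no plan for statistical hypothesis testing for this study", the affected comparisons are labelled exploratory or supportive, and the primary risk difference handles zeros exactly. All of this stands and sets the severity.

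It is also right that withholding the hazard ratio itself is ordinary practice, and that most withheld pairs would show little. Where the rule fires often, 0 vs 5 or more is rare.

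A further reply is that the Aalen-Johansen difference remains. On the natural reading of "Incidence rates and cumulative incidences will be calculated only for endpoints with at least 1 event in a treatment arm", one event in any arm is enough, so 0 vs 5 would still be displayed. This stands in part: the interval is unreliable with an empty arm, and the wording could also be read arm by arm.

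The reference in SAP 6.4.3 might be meant to take in all of 6.4.1. If so, the total-treatment and overall bleeding analyses would regain the exact difference, but the text does not say so.

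Three stronger readings are tempting, and the documents do not support them:

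- **Comparisons vanish exactly when the bleeding contrast is largest.** The trigger is a zero count. 0 vs 1 (1.4 points) is withheld, and 1 vs 12 (15.3 points) is reported. The statement is true only on the ratio scale.
- **Subgroup forest plots would keep only levels with events in both arms.** SAP 6.2.2.3 and 6.4.5 name no effect measure for the plots.
- **At rates of 3%, 2% and 1% the rule costs 21%, 41% and 73% of comparisons.** Those figures count 0 vs 0 pairs, which no rule could test.

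**Conclusion.** The point holds, and it is minor. The SAP withholds two computable tests together with an estimate that is not computable, so part of the exploratory and supportive time-to-event output depends on the result. The primary safety analysis is unaffected.

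The loss is about 3% to 8% per dose-placebo pair for the composite, and about 20% to 50% of pairs for outcomes at assumed rates of 3% to 1%. Few of the withheld pairs would fall below 10% by an exact test. The practical gap is the lack of an exact between-arm contrast for the total-treatment and overall bleeding analyses, as 6.4.3 is written, and for the efficacy endpoints and components.

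The figures assume 72 treated per arm, no censoring in the test illustrations, and planning rates carried over from the unconjugated compound. With 60 per arm the composite figures become 12.5%, 6.0% and 11.3% per pair.

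**What to change.** In SAP section 6:

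- Calculate log-rank and Gray's tests when the two compared arms combined have at least one event, with a permutation or exact p-value when events are few.
- When one arm is empty, report the hazard ratio as not estimable. A one-sided bound is optional.
- State that the looser condition means at least one event in any arm. Show an empty arm as 0 with an exact upper limit in place of the 2e formula.

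In SAP 6.4.3, 6.2.1 and 6.2.1.1, extend the exact risk difference of 6.4.1 to the total-treatment and overall bleeding analyses and to the efficacy endpoints and components. Name it as the contrast to read when an arm is empty, in preference to the Aalen-Johansen interval.

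The cost is a few sentences, a programming branch and some wide intervals in the output. Conduct and data collection do not change.

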6.1.1 Disposition

The following will be tabulated overall and/or by treatment group:

- Study sample sizes (All enrolled subjects)
- Study sample sizes by region, country, and site
- Subject disposition (by treatment group and overall)
- Number of subjects and primary reasons for screening failures
- Number of subjects and primary reasons for permanent discontinuation of study intervention (by treatment group and overall)

6.1.2 Demographic and Baseline Characteristics

Demographic and baseline characteristics include:

- Dialysis and ESRD disease characteristics obtained before the first study intervention administration
- Age groups
 - <60 years,
 60-75
 >75 years
 - <50yrs
 >=50-<60yrs
 >=60-<65yrs
 >=65-<70yrs
 >=70-<80yrs
 >=80yrs
 - <=65 years
 >65 years)

- BMI groups
 - Below 18.5 = underweight; 18.5 to <25.0 = healthy weight; 25.0 to <30.0 = overweight; >= 30.0 = obesity
 - 30 to <35: obesity class 1; 35 to <40: obesity class 2; >=40: obesity class 3
- Age, Weight, Height, BMI as continuous variables
- Gender, Ethnicity, Race
- Time since the start date for renal replacement therapy,

The continuous variables will be summarized using descriptive statistics, while counts and percentages will be provided for categorical variables. All analyses will be presented overall and by treatment group in both the FAS and SAF analysis sets. Other baseline characteristics may be added as deemed appropriate. No statistical tests will be performed to compare these characteristics across treatment groups.

Age for each participant will be defined as the number of years between informed consent date and birth date.

For summarizing race, if multiple races are recorded in the database, then 'multiple race' will be used in the summary table.

6.1.3 Definition of Baseline

In general, a baseline assessment will be the last non-missing value prior to the first administration of study intervention (Fesomersen or placebo) on Day 1. If Day 1 values are not available, last screening values will be used. Furthermore, if there is more than one assessment at the same timepoint, the baseline value will be the mean of the recorded measurements prior to the administration of study intervention.

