6.1 Study Intervention(s) Administered

Table 6-1: Study interventions administered

Arm Name	BAY 2976217	Placebo
Intervention Name	BAY 2976217	Placebo
Type	Drug	Placebo
Dose Formulation	solution for injection	solution for injection
Unit Dose Strength(s)	100 mg/mL	not applicable
Dosage Level(s)	40 mg, 80 mg or 120 mg (or	• •
3 ()	100 mg if dose reduction is	not applicable
	recommended by DMC)	• •
Route of	SC injection	SC injection
Administration	,	,
Use	Experimental	Placebo
Packaging and	Study intervention will be provided	Study intervention will be provided
Labeling	in 2 mL colorless vials.	in 2 mL colorless vials. Each vial
	Each vial will be labelled as	will be labelled as required per
	required per country requirement.	country requirement.
Current/Former	ION-957943	not applicable
Name(s) or Alias(es)	10.11 00.70 10	пос арриоавіо

DMC = Data Monitoring Committee, SC = Subcutaneous

BAY 2976217 is supplied in 2 mL clear, single-use injection glass vials as a solution. BAY 2976217 is a solution with a concentration of 100 mg/mL. The total content of the glass vial is approximately 1.05 mL, corresponding to 100 mg BAY 2976217. From the total 1.05 mL, 0.8 mL (i.e. 80 mg) are extractable volume and 0.25 mL (i.e. 25 mg) are overfill.

Placebo to BAY 2976217 is supplied in 2 mL clear, single-use glass vials as a solution with a content of 1.05 mL (0.8 ml extractable volume). Further details can be found in the handling instruction provided separately.

Different doses will be achieved by administering a different volume. For dosage regimen and planned duration of intervention see Section 4.1.

Study intervention will be administered any time from 15 minutes before the start of dialysis to 15 mins after the start of dialysis, when administered on a dialysis day.

Study intervention can be administered in the following SC injection areas:

- Abdomen (upper right, upper left, lower right, lower left)
- Thigh
- Outer area of upper arm

Note: Injection is not to be given within two inches (5cm) of any of the following: the umbilicus, the active reaction area of a previous injection, or in areas of the skin that are burned, reddened, inflamed, or swollen. Injections may be administered to a location that previously was involved in an injection site response provided that any symptoms have largely resolved.

07 JUL 2021 Page: 36 of 90

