8.2.1.4 AV access bleeding

Severity of bleeding at the dialysis access will be assessed approximately 15 minutes after removal of the dialysis needle(s) from the vascular access at the end of the dialysis session on the visit day (or from a dialysis session within the visit window if the visit is not conducted on a dialysis day) according to the following categories (exploratory bleeding score):

- "0" no access bleeding
- "1" slow oozing
- "2" overt bleeding

In the case the bleeding stops before the end of the 15-minute period after removal of the dialysis needle(s) from the vascular access (score 0), the assessment may be done prior to the end of the 15-minute period.

In case a catheter is used, the AV access bleeding is not applicable.

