8.5.1.1 PK, PD and immunogenicity sampling (all participants)

- Visit 5 will be conducted on a dialysis day. The first dose of study intervention will be administered on Visit 5, prior to the start of the dialysis session. Visit 5 plasma PK/PD samples will be drawn at timepoints described in Table 8–1. Dialysate effluent will be collected 15 minutes to 30 minutes after the start of dialysis, and during the final 30 minutes of dialysis. Visit 5 immunogenicity sample will be drawn pre-HD, before the first dose of study intervention.
- Visit 6 will be conducted the day after Visit 5, on a non-dialysis day. The Visit 6 plasma PK/PD sample will be drawn 22-32 hours after the first dose of Study intervention administration on Visit 5.
- Visit 10 will be conducted on a dialysis day. Dosing on Visit 10 will occur prior to the start of the dialysis session. Visit 10 plasma PK/PD samples will be drawn at timepoints described in Table 8–1. Dialysate effluent will be collected at 15 min to 30 min after the start of dialysis and during the final 30 minutes of dialysis. The total dialysis volume should be recorded.
- At Visit 12, Visit 14, Visit 16, Visit 18 (main treatment period) and Visits 23-27 (extended treatment period) plasma PK and PD, and immunogenicity (when applicable) sampling will be done before dosing (trough sample), at other visits sampling can occur at any time during the visit.
- At Visit 22, plasma PK and PD, and immunogenicity sampling will be done before dosing (trough sample) if the participant receives study intervention. In cases when the participant does not receive study intervention at Visit 22, sampling can occur at any time during the visit.

8.5.1.2 PK, PD and immunogenicity sampling, participants from the alternative PK&PD sampling group starting on a non-dialysis day

- For these participants, study intervention will be administered on a non-dialysis day preceding a scheduled dialysis day.
- Visit 5 will be conducted on a non-dialysis day preceding a scheduled dialysis day. The first dose of study intervention will be administered on Visit 5. Visit 5 plasma PK/PD samples will be drawn at timepoints described in Table 8–1. Immunogenicity samples will be drawn before the first dose of study intervention on Visit 5.
- Visit 6 will be conducted the day after Visit 5, on a dialysis day. The Visit 6 plasma
 PK/PD sample will be drawn 22-32 hours after the first study intervention

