At the end of the hemodialysis procedure, at specified time points, the filter and line (including drip chamber/air trap) will be examined by the hemodialysis nurse (or respective appropriate personnel) after rinsing the circuit. Clotting scores will be assigned as follows:

- "0" clean filter and no visible clots in the drip chamber/air trap
- "1" traces of coagulation in the filter and/or in the drip chamber/air trap
- "2" intermediate state between "1" and "3"
- "3" fully clotted extracorporeal system resulting in an interruption of the hemodialysis session

Adequate anticoagulation is defined by a SQCS of less or equal "1".

Overall score is the highest of the individual component scores:

Inspection Site	Category 0	Category 1	Category 2	Category 3
Drip chamber (also referred to as air trap)	No visible clots in the drip chamber	Trace (e.g fibrinous ring with no clot formation on venous chamber)	Intermediate (e.g clot formation on venous chamber, more than "1" but not fully clotted)	Fully clotted system (treatment cannot continue without new setup)
Dialyzer	Clean dialyzer	Trace (e.g blood stripes affecting less than approximately 5% of the fibers seen at the surface of the dialyzer)	Intermediate (e.g blood stripes affecting approximately 5% or more of the fibers seen at the surface of the dialyzer, but not fully clotted)	Fully clotted filter

Only one (highest) score will be documented in the eCRF.

The clotting score will be recorded as specified in the SoA. The dialyzer and drip chamber/air trap will be assessed for clotting score at the end of the dialysis session on the visit day (or from a dialysis session within the visit window if the visit is not conducted on a dialysis day).

For information on PD sampling see Section 8.5.

The study sponsors reserve the right not to conduct all or part of the above-mentioned analysis.

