10.6.1 Amendment 1: (29 SEP 2020)

This amendment is considered to be substantial based on the criteria set forth in Article 10(a) of Directive 2001/20/EC of the European Parliament and the Council of the European Union.

Overall Rationale for the Amendment

This amendment was prepared to address the change in the new contraception guidance as requested by Health Authorities. Additionally, the number of procedures and visits was decreased to reduce the burden on the participants. This reduction does not impact the participants' safety nor affect the benefit-risk assessment.

Key changes

Section # and Name	Description of Change	Brief Rationale
10.4 Contraceptive Guidance and Collection of Pregnancy Information	Contraception was changed into highly effective (removing the barrier method as example for contraception)	Request from Health Authorities
1.3. Schedule of Activities (SoA) + throughout the protocol	Visits 2, 3 and 4 removed; screening period shortened to 7 (+6) days with provision that some procedures can be done on more than one day	To reduce the burden on the participants. The visits are reduced during screening before randomization therefore there is no safety concern.

07 JUL 2021 Page: 82 of 90

Section # and Name	Description of Change	Brief Rationale
1.3 Schedule of Activities (SoA)	ECG assessments removed on Visits 5, 10, 14, 15, 16, 23, 24, 25, 26, 27, FU1	To reduce the burden on the participants. Frequent ECGs was initially deemed necessary for the documentation of efficacy outcomes. However, since the efficacy outcomes are mainly based on symptomatic events, the use of pre-planned ECGs is not expected to contribute to an adequate assessments of suspected outcomes. For unsuspected changes on the ECGs related to the study drug, the protocol requires 4 routine ECGs to be done during the main treatment phase.
1.3 Schedule of Activities (SoA), 8.2.3 Vital Signs	Post HD BP measurements changed from average of 3 blood pressure readings to one post HD BP measurement; temperature, pulse and heart rate measurements removed => vital signs comprise only post HD BP measurements.	To reduce the burden on the participants. The patients are seen at the center at least 3 times a week (9 hours/week) and post-HD blood pressure will be collected on a regular basis. Therefore, collection of vital signs is redundant.

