6.3.2.2 SQCS Analysis

The effect of Fesomersen on the clotting in the dialysis circuit will be assessed by the SQCS.

The clotting assessment will be conducted on the PD analysis set and will be presented according to treatment group. Clotting scores will be assigned as follows:

Clotting score	Definition
Clotting Score 0	Clean filter and no visible clots in the drip chambers
Clotting Score 1	For traces of coagulation in the filter and/or in the drip chambers
Clotting Score 2	Intermediate state between 1 and 3
Clotting Score 3	Fully clotted extracorporal system resulting in an interruption of the
	hemodialysis session

Table 6-1: Clotting scale score

Adequate anticoagulation is defined by an SQCS of less or equal "1".

The summary of each clotting score category will be presented in frequency and the percentage of patients by visits.

The overall score for individual subjects, which is the highest clotting score from all visits per data scope, will also be summarized. The overall clotting score will be analyzed for treatment comparison between each Fesomersen dose groups and placebo group using the Wilcoxon Rank Sum test.

The difference in the mean of SQCSs during the main treatment period between each of the Fesomersen groups and the placebo group will be displayed together with the corresponding 90% (and 95%) confidence intervals applying ANOVA with treatment group as factor.

Furthermore, the difference in the proportion of hemodialysis sessions with adequate anticoagulation during the main treatment period between each of the Fesomersen dose groups and the placebo group will be summarized with the corresponding 90% (and 95%) confidence intervals using the unstratified exact method with the standardized test statistic and inverting a two-sided test (Agresti and Min, 2000) as exploratory analysis.

Frequency of dialyzer filters usage will be analyzed through descriptive statistics.

Most severe clotting category

In order to examine the correlation of FXI activity level and clotting, a separate summary on the most severe clotting category will be provided for patients with average FXI activity ≤ 0.1 , ≤ 0.2 , ≤ 0.3 , ..., ≤ 1.0 U/mL for Fesomersen treated patients only.

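### The Visit 5 clotting score, read a few hours after the first injection, counts as an on-treatment session and dilutes the main-period mean and adequacy comparisons by about 9 to 10%

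*SAP*

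**What the plan says.** **Dose.** On dialysis days, Protocol 6.1 has: "Study intervention will be administered any time from 15 minutes before the start of dialysis to 15 mins after the start of dialysis". For the regular group, Protocol 8.5.1.1 adds: "The first dose of study intervention will be administered on Visit 5, prior to the start of the dialysis session".

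**Score.** The Schedule of Activities lists a clotting score at Visit 5. Protocol 8.6.2 fixes its timing: "The dialyzer and drip chamber/air trap will be assessed for clotting score at the end of the dialysis session on the visit day".

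**Window.** SAP 4.5.1 opens the main treatment period at the first dose, and SAP 4.5.2 opens the PA, TA and OA scopes on that date. For participants who enter the extension, SAP 4.5.1 closes the main period at the Visit 22 dose.

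**Analysis.** SAP 6.3.2.2 compares each dose group with placebo on three quantities:
- the mean SQCS over the main period (ANOVA with treatment group as the factor);
- the proportion of sessions with a score of 1 or less over the same period;
- each participant's overall score, "which is the highest clotting score from all visits per data scope" (Wilcoxon rank sum).

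It also tabulates the most severe category by band of average FXI activity, and score frequencies by visit. No visit is excluded.

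**Baseline.** The general rule in SAP 6.1.3 is that "a baseline assessment will be the last non-missing value prior to the first administration of study intervention (Fesomersen or placebo) on Day 1". It continues: "If Day 1 values are not available, last screening values will be used". Protocol 9.4.6.3 has its own rule for the clotting and access-bleeding scores: the mean over the screening week, set against an evaluation period at Visits 19 to 22.

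**The concern.** The drug lowers FXI by blocking its synthesis in the liver, so FXI already in the circulation has to decay before any effect can appear. A session that ends a few hours after the first injection tells us about the untreated state. Counting it among the treated sessions pulls each dose group towards placebo.

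The primary analysis is meant to speed Phase 3 dose selection (Protocol 4.1) and covers PK/PD (Protocol 9.4), so a diluted clotting contrast has some consequence. In the table by FXI band, a Visit 5 score taken before FXI has fallen can fix the most severe category of a participant whose average FXI later places them in a low band.

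**Working it through.** The plan gives no effect size, score distribution or power for SQCS, so there is no planning figure to reproduce. The sizes below follow from the visit schedule or from assumptions labelled as such.

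**1. Is Visit 5 effectively untreated?** The FXI half-life is about 50 h (Protocol 8.2.1.2). At least 9 hours a week over three sessions means about 3 h per session; Protocol 2.2.3.2 mentions a 4-hour session in the earlier dialysis study. If synthesis stopped completely at the injection, the fraction of FXI remaining after t hours would be 2^(−t/50):
- 3 h: 95.9%
- 4 h: 94.6%
- 5 h: 93.3%

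These are lower bounds, because synthesis will not stop at once.

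**2. How many scored sessions?** The Schedule of Activities gives V5, V8, V10, V12, V14, V16, V18, V19, V20, V21 and V22, so k = 11. In extension entrants the end-of-session V22 score follows the V22 dose, which closes the main period, so k = 10. In non-entrants the main period ends 28 days after the last dose. With that dose at V18 on Day 141, this is Day 169, the nominal V22 day, and V22 has a +5-day window. Its place is therefore not secure there either.

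**3. Mean score and proportion of adequate sessions.** With complete data and no effect at Visit 5, the difference with Visit 5 included equals (k − 1)/k times the difference without it, whatever the later time course:
- k = 11: 10/11 = 0.909, a loss of 9.1%
- k = 10: 9/10 = 0.900, a loss of 10%

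The alternative PK&PD group (target 24 to 40 participants) has no Day 1 dialysis session. If these participants contribute no Visit 5 score, are spread evenly over the arms and respond alike, the whole-arm loss is (1 − a)/k, where a is their share. For a = 24/288 = 0.083 it is 8.3% (k = 11) or 9.2% (k = 10). For a = 40/288 = 0.139 it is 7.8% or 8.6%.

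**4. Highest score.** Let q0 and q1 be the untreated and treated per-session risks of a score of 2 or more. With independent sessions, the difference in the share of participants whose highest score is 2 or more is
- without Visit 5: (1 − q1)^(k−1) − (1 − q0)^(k−1)
- with Visit 5: the same expression times (1 − q0)

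The relative loss therefore equals q0, which the documents do not give. The table assumes that the drug halves the risk, with k = 11. Its last column is a simulation with a latent within-participant correlation of 0.5.

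| q0 | Without V5 | With V5 | Loss, independent | Loss, correlated |
|---|---|---|---|---|
| 2% | 0.087 | 0.086 | 2% | 6% |
| 10% | 0.250 | 0.225 | 10% | 11% |
| 30% | 0.169 | 0.118 | 30% | 18% |

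**5. Power for the mean score.** Take 60 per arm, a two-sided 10% level, and an effect with 80% power when Visit 5 is left out. Including Visit 5 multiplies the effect by (k − 1)/k and changes the SD of a participant's mean, √(ρ + (1 − ρ)/m), from m = k − 1 to m = k sessions. For ρ from 0 to 0.8, power falls to about 77% to 72%.

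**The case against.** The strongest reply is that little depends on this. SQCS is an exploratory pharmacodynamic endpoint, and Protocol 9.1 plans no hypothesis testing. All arms are handled alike, so the error cannot favour the drug. The by-visit table shows Visit 5 separately, and the evaluation-period analysis in Protocol 9.4.6.3 leaves it out. An average over the main period includes onset by definition. The separate output specifications, not available here, may already deal with Visit 5. All of this limits the weight of the point. It does not remove the dilution from the three comparisons as written, and a rule that changes an estimate belongs in the SAP.

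Four stronger readings are tempting, and the documents do not support them:
- *The baseline rule causes the problem and a valid Day 1 baseline is lost.* None of the three comparisons uses a baseline. Visit 5 enters through the period and scope definitions. Protocol 9.4.6.3 already places the clotting and access-bleeding baseline in screening.
- *Every active participant has one untreated session in 11.* The alternative group has no Day 1 session, and extension entrants have 10 scored sessions in the period.
- *The highest-score comparison loses a definite, large share.* Under independence the loss simply restates the assumed untreated risk. The planned test also ranks scores from 0 to 3 and does not dichotomise at 2.
- *Visit 5 blood pressure and access bleeding should be removed as well.* These are safety measures and Visit 5 is the first reading after an injection. The FXI half-life says nothing about an acute response to an injection.

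**Conclusion.** The point holds in a limited form. In the regular-sampling group an essentially untreated session is counted as treated in the mean SQCS, the proportion of adequate sessions, the highest score and the table by FXI band. The 9 to 10% dilution of the first two rests on complete data and no effect at Visit 5; in a participant who stops early, Visit 5 is a larger share of the sessions. For the highest score only the direction, towards no difference, is secure. The primary bleeding endpoint is untouched. This is a modest flaw in an exploratory analysis, worth correcting because the correction is cheap.

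**What to change.** In SAP 6.3.2.2, state for all arms that SQCS values from the Visit 5 dialysis session are excluded from the main-period mean, the adequate-anticoagulation proportion, the highest score and the most-severe-category summary by FXI activity. Keep Visit 5 in the by-visit table, and repeat the comparisons with it included as a sensitivity analysis.

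In the same edit:
- assign the end-of-session Visit 22 score explicitly to one period, for extension entrants and non-entrants;
- say how a score recorded against Visit 5 in the alternative PK&PD group is handled;
- keep the screening baseline for SQCS and reconcile SAP 6.1.3 (last value) with Protocol 9.4.6.3 (screening mean). The two can differ for participants enrolled before Amendment 1, who also had Visits 2 to 4;
- leave Visit 5 blood pressure and access bleeding in the safety summaries.

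The cost is a few sentences and no new data. The downside is one fewer session per participant in these summaries and a small departure from using every visit in the period.
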